**Evaluation of Omega-3 Polyunsaturated Fatty Acids Plus Low-dose
Aspirin Daily Supplementation in Surgical Therapy to Treat Generalized
Aggressive Periodontitis: Randomized Controlled Clinical Trial**

NCT03093207

May 15, 2017

Study Protocol

Periodontal destruction results mainly from the exacerbated host inflammatory response to the bacterial challenge. For this reason, research involving the modulation of host response has been developed aiming to facilitate the resolution of inflammation, as well as to promote tissue repair and periodontal stability. Recently, the use of omega-3 polyunsaturated fatty acids (Ω -3 PUFA) and low-dose acetylsalicylic acid (ASA) was related to the production of enhanced lipidic mediators and to better clinical outcomes in the treatment of chronic periodontitis. Thus, the aim of the present randomized controlled clinical trials was to evaluate the use of 900 mg Ω -3 PUFA and 100 mg ASA for 180 days as adjuvants to the treatment of generalized aggressive periodontitis (GAgP). Thirty-four GAgP patients previously submitted to NST with residual pockets were selected and underwent open flap debridement associated with Ω -3 PUFA 3 and ASA (n=17) or placebo (n=17). After 6 months, both therapies led to decreased PD ($p > 0.05$), but only the test group had CAL gain in the intergroup comparison ($p = 0,02$), as well as presented less gingival recession ($p = 0,03$), decreased dentin hypersensitivity ($p = 0,01$), lower consumption of analgesics ($p = 0,02$) and significant intragroup reduction of IL-10 ($p < 0.05$). The microbiological analysis of the residual pockets did not reveal significant changes compared to baseline. It was concluded that the proposed new therapy brought clinical benefits to the surgical treatment of GAgP patients.

Statistical Analysis Plan

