Mean and standard deviation were calculated in each of the parameters. PI, BoP, PD, CAL, and GR were submitted to the Shapiro-Wilk test to evaluate the distribution of these data, and then subjected to the variance test for both intra- and intra-group comparison. In addition, the number of pockets $\geq 5\text{mm}$, the frequency of closure of these pockets, the mean reduction in PS and the gain in CAL of these pockets were assessed before and after the therapy by performing intra- and inter-group analyzes. IBM SPSS software was used to data analyses. The concentration of each cytokine/microorganism were analyzed by test of variance for intra and intergroup comparison.

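### The intergroup test of cytokine and microorganism concentrations should state and use the baseline value as a covariate; moving to ranks gains further power only if the data have heavy tails.

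*Combined protocol and SAP*

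**What the plan says.** The Statistical Analysis Plan section covers all laboratory measurements in its last sentence: "The concentration of each cytokine/microorganism were analyzed by test of variance for intra and intergroup comparison". It does not say whether this is an analysis of follow-up values, of changes, or a repeated-measures model. It gives no baseline covariate, transformation, rank method or rule for values below detection.

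The distribution check is confined to five clinical measures: "PI, BoP, PD, CAL, and GR were submitted to the Shapiro-Wilk test to evaluate the distribution of these data". Concentrations are not listed, and no action is tied to the outcome of the check even for those five. Summaries are by moments throughout: "Mean and standard deviation were calculated in each of the parameters".

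The Study Protocol section, which already contains results, reports two findings on concentrations. One is a within-arm cytokine finding, "significant intragroup reduction of IL-10". The other is a null: "The microbiological analysis of the residual pockets did not reveal significant changes compared to baseline". It gives no between-arm p value for any concentration. There were 17 patients in each arm.

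**The concern.** The between-arm comparison is the one that uses the randomisation. With 17 per arm it has little power to spare, and the plan does not say that it uses the baseline measurement in the most efficient way. That issue does not depend on the shape of the data.

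A second issue does. Mean and SD summaries, with no transformation named, suggest analysis on the measured scale. If concentrations have long right tails, a few large values inflate the variance and a real shift can be missed. At stake is how much weight a null concentration result can carry, in particular the microbiology sentence.

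**Working it through.** **Inputs from the documents.** 17 per arm; follow-up at 6 months; the wording quoted above. There is no power, alpha or sample-size figure to reproduce. For orientation, with normal data and a two-sided 5% test, 17 per arm gives 65% power for a difference of 0.8 SD and 83% for 1.0 SD.

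**Inputs assumed (none is in the documents).** Two-sided 5%; a two-fold reduction in one arm; baseline-to-follow-up correlation 0.5, varied from 0 to 0.7; no dropout. Six shapes: log-normal with log-SD 0.5, 1.0, 1.5, and gamma with skewness 1.4, 2.0, 2.8. Each setting used 20,000 simulated trials.

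**Model.** Follow-up = a + b × group + c × baseline + error. A follow-up test fixes c = 0. A change test, which is the group-by-time term of a two-visit repeated-measures ANOVA, fixes c = 1. ANCOVA estimates c. With equal variances the error variances are proportional to 1, 2(1 − ρ) and 1 − ρ². At ρ = 0.5 these are 1, 1 and 0.75. Rank ANCOVA fits the same model after ranking follow-up and baseline across all 34 patients.

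**Intergroup power (%), two-fold reduction, correlation 0.5**

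| Shape | Raw follow-up | Raw change | Raw ANCOVA | Rank ANCOVA |
|---|---|---|---|---|
| Log-normal 0.5 | 96 | 82 | 98 | 99 |
| Log-normal 1.0 | 34 | 23 | 40 | 57 |
| Log-normal 1.5 | 11 | 8 | 13 | 30 |
| Gamma 1.4 | 76 | 57 | 84 | 80 |
| Gamma 2.0 | 44 | 31 | 51 | 46 |
| Gamma 2.8 | 21 | 17 | 24 | 23 |

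**Step 1: baseline adjustment, raw scale kept.**
- Raw ANCOVA minus raw follow-up: 2, 6, 2, 8, 7, 3 points.
- Raw ANCOVA minus raw change: 16, 17, 5, 27, 20, 7 points.
- The lead over change depends on direction. For a doubling, the change test has 98, 36 and 11% (log-normal) and 50% (gamma 2.0). ANCOVA has about the same power as for a halving, so it leads by only 98 − 98 = 0, 40 − 36 = 4, 13 − 11 = 2 and 51 − 50 = 1.
- Where it loses: about 1 to 2 points against follow-up at correlation 0, and up to 69 − 66 = 3 points against change for a doubling at correlation 0.7 (gamma 2.0).

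**Step 2: from raw ANCOVA to rank ANCOVA.**
- Log-normal 1.0 and 1.5: 57 − 40 = 17 and 30 − 13 = 17, or about 16 to 17 before rounding. Log-normal 0.5: 99 − 98 = 1.
- Gamma: 80 − 84 = −4, 46 − 51 = −5, 23 − 24 = −1. At correlation 0.7, skewness 2.0: 60 − 66 = −6.
- The gain is therefore a matter of heavy tails, not of right skew in general.

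**Sensitivity, raw follow-up against rank ANCOVA.**
- Correlation 0.3: 34 vs 50% (log-SD 1.0), 12 vs 25% (1.5), 44 vs 41% (gamma 2.0).
- Correlation 0.7: 34 vs 72%, 12 vs 39%, 44 vs 60%.
- With 30% of baseline values undetectable and tied lowest (correlation 0.5): 32 vs 50%, 11 vs 27%, 44 vs 46%.

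**Type I error.** Raw tests 2.1 to 5.2%; rank ANCOVA 4.9 to 5.5%. Nothing is inflated.

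**Change over time.** Within one arm of 17, raw paired t against Wilcoxon signed-rank is 50 vs 66% (log-SD 1.0), 15 vs 34% (1.5) and 65 vs 64% (gamma 2.0). If the test pools all 34 and both arms halve, it is 82 vs 94%, 32 vs 62% and 95 vs 94%.

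**The case against.** The case against has real force.

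- **The raw scale is inferred from silence.** The wording excludes neither logged values nor a rank analysis of variance, and the documents give no spread, shape, correlation or effect size. Across the settings tried, rank ANCOVA ranges from 6 points below raw follow-up (gamma, correlation 0) to 72 − 34 = 38 points above it (log-SD 1.0, correlation 0.7). This stands: no single power figure can be given for this trial.
- **The test may already use baseline.** A reader might infer that the intergroup test ignored baseline. A repeated-measures ANOVA is an equally natural reading, and its group-by-time term uses baseline through the change. This also stands, but it does not remove the point, because ANCOVA generally does as well as or better than the change test too, with the small exceptions in step 1.
- **Two gains are easily merged.** At log-SD 1.0 and correlation 0.5, ranks without baseline reach 47%, between about 35% for raw follow-up and 57% for rank ANCOVA. Much of the total gain is baseline adjustment and owes nothing to tails. The steps are kept apart above for that reason.
- **Choosing log or ranks from the data would be unsound.** Results are already reported, and 34 patients cannot reliably separate a log-normal from a gamma shape. Accepted: the remedy uses one fixed rule.
- **Little hangs on it.** The stated clinical benefits rest on attachment level, recession, hypersensitivity and analgesic use, none of which is a concentration. Accepted, and it limits the severity.

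**Conclusion.** The point holds in two parts of different strength. First, the plan does not specify the concentration analysis, and under either natural reading the intergroup test would generally be improved by a baseline covariate: about 2 to 8 points over raw follow-up and about 5 to 27 over raw change, for a two-fold reduction at correlation 0.5. The gain over change is much smaller for an increase, and the gain over follow-up vanishes at correlation 0. Second, only if tails are heavy, ranks add about 16 to 17 points beyond that.

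A reader might go further and infer that the raw-scale test makes the IL-10 reduction unreliable, or that a treatment effect on bacteria was missed. The documents support neither. Type I error is not inflated, so the IL-10 result is untouched on this ground. Nothing shows that the tails are heavy or that any effect existed. What follows is narrower: the microbiology sentence is not evidence of no change or of no difference between arms. An intergroup null would stay weak after the change, since rank ANCOVA has 57% power at log-SD 1.0 and 30% at 1.5. Severity is minor to moderate.

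**What to change.** For the intergroup comparison of each cytokine and microorganism, state one rule fixed without looking at the data: ANCOVA on the ranks of the follow-up concentration, with group and ranked baseline concentration as terms, and non-detects as tied lowest ranks. Do not select log or rank from the observed distribution.

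Report medians and interquartile ranges by arm. If a Hodges-Lehmann difference is shown, label it descriptive, because it is unadjusted and does not correspond to the adjusted test. Treat within-arm tests as descriptive, using the Wilcoxon signed-rank test if they are kept. State whether the microbiology comparison with baseline was made per arm or over both arms together.

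The work is a change of wording and a rerun on existing data. The price is results on ranks rather than mean differences and, if the data are gamma-like, some power: up to about 6 points against raw ANCOVA, up to about 9 against a raw change test of a doubling at correlation 0.7 (69 − 60), and 3 to 6 against raw follow-up at correlation 0.
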